9.3.2.11 Treatment Period – Month 7 Visit (Week 28)

- Vital signs
 - sitting blood pressure and heart rate
- Eye and Vision Exams:
 - ETDRS BCVA
- Laboratory Procedures
 - clinical chemistry
- AE monitoring and AE recording since last visit
- Concomitant Medication recording as needed since last visit
- Collect returned used supplies and review medication use since last visit
- Dispense 1 month supply of study medication kits

9.3.2.12 Treatment Period – Month 8 Visit (Week 32)

- Vital signs
 - sitting blood pressure and heart rate
- Eye and Vision Exams:
 - ETDRS BCVA
- Laboratory Procedures
 - hematology
 - clinical chemistry
- AE monitoring and AE recording since last visit
- Concomitant Medication recording as needed since last visit
- Collect returned used supplies and review medication use since last visit
- Dispense 1 month supply of study medication kits

9.3.2.13 Treatment Period – Month 9 Visit (Week 36)

- Vital signs
 - sitting blood pressure and heart rate measurements
- Eye and Vision Exams:
 - ETDRS BCVA
 - slit-lamp biomicroscopy
 - intraocular pressure
 - dilated indirect ophthalmoscopy
 - SD OCT
 - fundus photography
 - ERG (at select sub-study sites)
 - OCT-A (at select sub-study sites)
- Laboratory Procedures
 - clinical chemistry
 - urinalysis

- AE monitoring and AE recording since last visit
- Concomitant Medication recording as needed since last visit
- Collect returned used supplies and review medication use since last visit
- Dispense 1 month supply of study medication kits
- Dispense instructions and kit for subject to perform home fecal occult blood specimen collection

9.3.2.14 Treatment Period – Month 10 Visit (Week 40)

- Vital signs
 - sitting blood pressure and heart rate
- Eye and Vision Exams:
 - ETDRS BCVA
- Laboratory Procedures
 - hematology
 - clinical chemistry
- AE monitoring and AE recording since last visit
- Concomitant Medication recording as needed since last visit
- Collect returned used supplies and review medication use since last visit
- Dispense 1-month supply of study medication kits

9.3.2.15 Treatment Period – Month 11 Visit (Week 44)

- Vital signs
 - sitting blood pressure and heart rate
- Eye and Vision Exams:
 - ETDRS BCVA
- Laboratory Procedures
 - clinical chemistry
- AE monitoring and AE recording since last visit
- Concomitant Medication recording as needed since last visit
- Collect returned used supplies and review medication use since last visit
- Dispense 1-month supply of study medication kits

9.3.2.16 Treatment Period – Month 12 End of Treatment Visit (Week 48)

- 12 Lead ECG (prior to vital signs and blood draws)
- Weight and temperature
- Vital signs
 - sitting blood pressure and heart rate measurements
- Eye and Vision Exams:
 - ETDRS BCVA
 - slit-lamp biomicroscopy
 - intraocular pressure
 - dilated indirect ophthalmoscopy
 - SD OCT
 - fundus photography (and UWF fundus photography at select sub-study sites)

- fluorescein angiography (or UWF fluorescein angiography at select sub-study sites)
- ERG (at select sub-study sites)
- OCT-A (at select sub-study sites)
- Laboratory Procedures
 - urine pregnancy test
 - hematology
 - clinical chemistry
 - urinalysis
 - biomarker blood sampling
- AE monitoring and AE recording since last visit
- Concomitant Medication recording as needed since last visit
- Collect returned used supplies and review medication use since last visit
- Dispense instructions and kit for subject to perform home fecal occult blood specimen collection

9.3.3 Activities to be conducted at the Homecare nurse visit

Homecare nurse visits scheduled for Screening, Months 3, 6, 9 and 12 should be conducted within 1 week after the corresponding site visit. The Follow-up homecare visit occurs 4 weeks ± 3 days after the EOT visit at the site. Nurse visits will likely occur at subject's home; however alternate locations acceptable to the subject are allowed (e.g. investigative site).

Investigative sites will distribute instructions and kits for the subject to perform home fecal occult blood specimen collection and shipping to the Central Laboratory; nurses will review status of specimen collection and shipping with subjects on corresponding homecare visits.

During homecare nurse visits, if any change in status, the nurse will contact the Investigator, so that the Investigator can assess for any new adverse event or change in status of existing adverse event, and document and report accordingly.

9.3.3.1 Screening Visit

- Body systems assessment
- Review Status of fecal occult blood testing

9.3.3.2 Treatment Period – Month 3 Visit (Week 12)

- Body systems assessment

9.3.3.3 Treatment Period – Month 6 Visit (Week 24)

- Body systems assessment
- Review status of fecal occult blood testing

9.3.3.4 Treatment Period – Month 9 Visit (Week 36)

- Body systems assessment
- Review status of fecal occult blood testing

9.3.3.5 Treatment Period – Month 12 Visit (Week 48)

- Body systems assessment
- Review status of fecal occult blood testing

9.3.3.6 Follow-up Period -1 Month (4 weeks) Post-Treatment Visit (Week 52)

- Medical history since last visit
- Body systems assessment

10 ADVERSE EVENTS

10.1 Definitions

10.1.1 Adverse Events (AEs)

An adverse event (AE) is any untoward medical occurrence in a patient or trial subject administered a drug or biologic (medicinal product) or using a medical device; the event does not necessarily have a causal relationship with that treatment or usage.

AEs include the following:

- All suspected adverse medication reactions.
- All reactions from medication overdose, abuse, withdrawal, sensitivity, or toxicity.
- Apparently unrelated illnesses, including the worsening of a preexisting illness (see paragraph below on Preexisting Conditions).
- Injury or accidents. Note that if a medical condition is known to have caused the injury or accident (e.g., a fall secondary to dizziness), the medical condition (dizziness), the accident (e.g., fall secondary to dizziness), and any adverse outcome (e.g., hip fracture secondary to the fall) should be reported as three separate adverse events.
- Abnormalities in physiological testing or physical examination findings that require clinical intervention or further investigation (beyond ordering a repeat [confirmatory] test).
- Laboratory abnormalities that require clinical intervention or further investigation (beyond ordering a repeat [confirmatory] test) unless they are associated with an already reported clinical event. Laboratory abnormalities associated with a clinical event (e.g., elevated liver enzymes in a subject with jaundice) should be described under Comments on the report of the clinical event (e.g., jaundice) rather than listed as a separate adverse event.

Procedures – Diagnostic and therapeutic non-invasive and invasive procedures, such as surgery, should not be reported as adverse events. However, the medical condition for which the procedure was performed should be reported if it meets the definition of an AE. For example, an acute appendicitis that begins during the adverse event reporting period should be reported as the adverse event and the resulting appendectomy noted under Comments.

Preexisting Conditions – In this trial, a preexisting condition (i.e., a disorder present before the adverse event reporting period) should not be reported as an AE unless the condition worsens or episodes increase in frequency during the AE reporting period.

Abnormal Test Findings – All laboratory test results will be reviewed by the Investigator. The Investigator will utilize his/her judgment in determining if out of range laboratory values are clinically significant and should denote this using the abbreviation “CS” on the laboratory report for source documentation. Laboratory tests that are labeled as clinically significant should be reported as AEs, either separately or as part of a description of a symptomatic AE. If there are significant changes in a laboratory report from a previous visit that are determined to be clinically significant, these should also be reported as AEs. Any abnormal laboratory value which requires treatment or further diagnostic testing and/or results in discontinuation from study should be reported as AEs.

10.1.2 Serious Adverse Events (SAEs)

Each adverse event is to be classified by the Investigator as SERIOUS or NONSERIOUS. An adverse event that meets one or more of the following criteria/outcomes is classified as serious:

- Results in death
- Is life -threatening (see paragraph below on Life-threatening)
- Requires in -patient hospitalization or prolongation of existing hospitalization (see paragraph below on Hospitalization)
- Results in persistent or significant disability/incapacity (see paragraph below on Disability)
- Is a congenital anomaly/birth defect

Important adverse events that may not result in death, be life-threatening, or require hospitalization may be considered SAEs when, based upon appropriate medical judgment, they may jeopardize the patient or subject or may require medical or surgical intervention to prevent one of the outcomes listed above.

The term serious also includes any other event that the Investigator or Sponsor judges to be serious or which is defined as serious by the regulatory agency in the country in which the event occurred. If there is any doubt whether the information constitutes an AE or SAE, the information is to be treated as an SAE.

Life-threatening – Any AE that places the subject at immediate risk of death from the event as it occurred. A life-threatening event does not include an event that might have caused death had it occurred in a more severe form but that did not create an immediate risk of death as it actually occurred. For example, drug-induced hepatitis that resolved without evidence of hepatic failure would not be considered life threatening, even though drug-induced hepatitis of a more severe nature can be fatal.

Hospitalization – Hospitalization is defined as an overnight admission with observation of a minimum of 24 hours. A hospitalization planned before the start of the study for a preexisting condition that has not worsened does not constitute an SAE (e.g., elective hospitalization for a

total knee replacement due to a preexisting condition of osteoarthritis of the knee that has not worsened during the course of the study).

Disability – Defined as a substantial disruption in a person's ability to conduct normal life functions.

10.1.3 Severity

The Investigator will use the adjectives MILD, MODERATE, or SEVERE to describe the maximum intensity of the adverse event. For purposes of consistency, these intensity grades are defined as follows:

MILD:	Does not interfere with subject's usual function
MODERATE:	Interferes to some extent with subject's usual function
SEVERE:	Interferes significantly with subject's usual function

Note the distinction between the gravity and the intensity of an adverse event. **Severe** is a measure of intensity; thus, a **severe** reaction is not necessarily a **serious** reaction. For example, a headache may be severe in intensity, but would not be classified as serious unless it met one of the criteria for serious events listed above.

10.2 Eliciting Adverse Event Information

The Investigator is to report all directly observed AEs and all AEs spontaneously reported by the study subject. In addition, each study subject will be questioned about AEs at each site visit following the initiation of treatment.

10.3 Reporting

Each AE is to be classified by the Investigator as SERIOUS or NONSERIOUS. This classification of the gravity of the event determines the reporting procedures to be followed. If an SAE occurs, expedited reporting will follow local and international regulations, as appropriate.

All AEs that occur in study subjects during the adverse event reporting period specified in the protocol must be reported, WHETHER OR NOT THE EVENT IS CONSIDERED MEDICATION RELATED.

10.3.1 Reporting Period

The AE reporting period for this study begins from the time of informed consent and ends at the final protocol required visit.

IN ADDITION, any known untoward event that occurs subsequent to the AE reporting period that the Investigator assesses as possibly or probably related to the study medication should also be reported as an AE.

10.3.2 Reporting AEs

NONSERIOUS AEs are to be reported on the adverse event case report forms.

10.3.3 Reporting SAEs

Serious adverse events should be reported on both the clinical trial adverse event CRF and the Serious Adverse Event Report Form.

Note: Where the same data are collected, the forms must be completed in a consistent manner. For example, the same AE term should be used on both forms.

Any SAE, regardless of causal relationship, must be reported to the Sponsor within 24 hours after the Investigator becomes aware of the SAE by completing and sending an SAE report form. Compliance with this time requirement is essential so that the Sponsor may comply with its regulatory obligations.

The initial SAE report should be completed as fully as possible but should contain, at a minimum:

- A description of the event and the reason why the event is categorized as serious
- Subject identification number
- Investigator's name and site identification number
- Name of the suspected medicinal product (not applicable for double-masked studies)
- Causality assessment

Follow-Up information relating to an SAE must be reported to the clinical safety contact at the Sponsor within 24 hours of receipt by the Investigator by sending a completed SAE report form with new information. The subject should be observed and monitored carefully until the condition resolves or stabilizes.

All deaths are to be thoroughly investigated and reported. Autopsy reports are to be obtained, if possible.

The Sponsor and/or its designee are responsible for reporting SAEs to all applicable regulatory agencies and the central ethics committees within the required timeline.

The Investigator is responsible for submitting required safety information to their local IRB. This information includes but is not limited to any safety alert letter received from the Sponsor and any SAEs occurring at their site.

10.3.4 Relationship to Study Medication

The causal relationship of the AE to study drug will be assessed by both the Investigator and the Sponsor. The following definitions will be used in assessment.

Probably Related: The AE follows a reasonable temporal sequence from the time of drug administration. It follows a known response pattern to the study drug. The AE cannot be reasonably explained by other factors such as the subject's clinical state, therapeutic interventions, or concomitant drugs.

Possibly Related: The AE follows a reasonable temporal sequence from the time of drug administration, but could have been produced by other factors such as the subject's clinical state, other therapeutic interventions, or concomitant drugs.

Unrelated: The AE does not follow a reasonable temporal sequence from administration of the product or the AE is clearly related to other factors such as the subject's clinical state, other therapeutic interventions, or concomitant drugs administered to the subject.

10.3.5 Follow-Up of Unresolved Events

All AEs should be followed until they are resolved or the Investigator assesses them as chronic or stable or the subject's participation in the trial ends (i.e., until a final report is completed for that subject).

In addition, all serious adverse events and those nonserious events assessed by the Investigator as possibly or probably related to the study medication should continue to be followed even after the subject's participation in the trial is over. Such events should be followed until they resolve or until the Investigator assesses them as "chronic" or "stable."

10.4 Exposure *In Utero*

If any study subject becomes or is found to be pregnant while receiving study medication during the treatment period or within 30 days of discontinuing the study medication, the Investigator is to submit this information on a Pregnancy Notification Cover Sheet along with a completed Serious Adverse Event Form. This must be done irrespective of whether an AE has occurred. Pregnancy during this time frame of the female partner of a male subject should also be reported. To ensure subject safety, each pregnancy must be reported to the Sponsor's Medical Monitor or CRO designee within 24 hours of awareness of the pregnancy.

If the pregnancy of a female study participant is discovered during the study, study medication should be discontinued.

The Investigator will follow the subject (or female partner of a male subject) until completion of the pregnancy and will follow the neonate up to 1 month of birth.

Within 24 hours of awareness, Investigator sites will notify the Sponsor's Medical Monitor or CRO designee of abnormal pregnancy outcomes. Normal outcomes may be reported within 5 days of awareness. Reporting of outcome will be provided on the Pregnancy Reporting Form.

In addition to reporting the outcome on the Pregnancy Reporting Form, if the outcome of the pregnancy meets the criteria for immediate classification as a SAE (i.e., spontaneous abortion, stillbirth, neonatal death within one month of birth, or congenital anomaly [including that in an aborted fetus]), the Investigator should also follow the procedures for reporting a SAE within 24 hours of awareness.

Additional information about pregnancy outcomes follows:

- Note that "spontaneous abortion" includes miscarriage and missed abortion.
- All neonatal deaths that occur within one month of birth should be reported, without regard to causality, as SAEs. In addition, any infant death after one month that the Investigator assesses as possibly or probably related to the in utero exposure to the study medication should also be reported.
- In the case of a live birth, the "normality" of the newborn can be assessed at time of birth.

- The “normality” of an aborted fetus can be assessed by gross visual inspection unless there are pre-abortion laboratory findings suggestive of a congenital anomaly.

11 DATA ANALYSIS

11.1 Sample Size Determination

Estimates for sample size calculations are derived from published data from the analysis of the effect of ranibizumab (Lucentis) and aflibercept (Eylea) intravitreal administration regimens on DR severity score in the RISE/ RIDE studies and VIVID/VISTA studies, respectively, in which at least 28-46% of subjects improved by ≥ 2 steps after 12 months of treatment.

With 45 evaluable subjects per treatment group, the study has $>85\%$ power (based on Fisher’s Exact Test and a 2-sided alpha =0.05) to demonstrate a statistically significant improvement in percent of subjects improving by ≥ 2 steps on the ETDRS severity scale, assuming underlying rates for active and placebo of 30% and 5%, respectively. Assuming 10% drop-out/non-evaluable rate, a sample size of 50 subjects per treatment arm (approximately 150 total) has been selected.

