8.3.2 Randomization and Allocation to Treatment Group

Approximately 150 subjects will be treated in the study.

Using a central IWRS randomization system, eligible subjects will be assigned in a double-masked fashion 1:1:1 to one of the 3 treatment groups. To maintain balance between treatment groups with respect to DR severity, randomization will be stratified by Screening ETDRS DRSS (levels 43, 47 and 53). The number of study eyes randomized with Screening ETDRS DRSS level 43 will be capped at 50.

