11.7 Efficacy Analyses

All efficacy endpoints are listed in [Sections 5.5](#) and [5.6](#). All efficacy data will be summarized by treatment group and time point using appropriate descriptive statistics. Summaries will be presented for both the MITT and PP populations. Due to the small number of subjects that are expected to be enrolled at each center, all summaries and analyses will be performed using data pooled across centers.

The primary hypotheses to be tested is that AKB-9778 15mg twice daily and AKB-9778 15mg once daily will be superior to placebo in the improvement of DR as measured by the ETDRS severity scale change from baseline at 12 months. Specifically, the primary endpoint is the

percentage of subjects with an improvement in study eye severity of DR (ETDRS DR Severity Score or DRSS) of ≥ 2 steps at Month 12 without need for treatment of PDR or DME (by IVT, laser, or vitrectomy) in the study eye. The primary hypotheses will be tested in the MITT population using a Fisher's Exact Test with a 2-sided 5% significance level. To adjust for multiplicity, a pre-specified testing order will be used. AKB-9778 15mg twice daily will be tested first, and AKB-9778 15mg once daily will be tested second. Details of how missing data will be handled for the primary endpoint, along with sensitivity analyses to assess the impact of missing data will be outlined in the statistical analysis plan (SAP).

Secondary and exploratory endpoints will be analyzed without adjustment for multiplicity, and all inferential analyses will use a 2-sided 5% significance level. Continuous variables will be analyzed using ANCOVA models and/or repeated measures mixed effect models and dichotomous variables will be analyzed using the same approach as outlined for the primary endpoint. Details of how missing data will be handled for secondary and exploratory endpoints will be provided in the SAP.

Exploratory analyses will be conducted to understand the relationship between exposure and response and details of these analyses will be outlined in the SAP.

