## **10.1 Primary Efficacy Endpoint Analysis**

The primary hypotheses to be tested is that AKB-9778 15 mg twice daily and AKB-9778 15 mg once daily will be superior to placebo in the improvement of DR as measured by the ETDRS severity scale change from baseline at 48 weeks. Specifically, the primary endpoint is the percentage of subjects with an improvement in study eye severity of DR (ETDRS DRSS) of  $\geq 2$  steps at 48 weeks without need for treatment of PDR or DME (by IVT, laser, or vitrectomy) in the study eye. DRSS scores used for all analyses will be obtained from final adjudicated grading by the central reading center (Fundus Photograph Reading Center for the standard field images).

The primary hypotheses will be tested in the MITT population using a Fisher's Exact Test with a 2-sided 5% significance level. AKB-9778 15 mg twice daily will be tested first. If this is found to be statistically significant, then AKB-9778 15 mg once daily will be tested for statistical significance, at the same significance level. Cochran-Mantel-Haenszel (CMH) test stratified for baseline ETDRS DRSS (levels 4, 5 and 6) will also be used for testing primary hypothesis in the MITT population. Missing data will be imputed using LOCF; baseline values will not be carried forward.

As a sensitivity analysis, primary hypothesis will be tested using Fisher's Exact test, and CMH test stratified for baseline ETDRS DRSS (levels 4, 5 and 6) on OC in the PP population.

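### The >85% power is a per-comparison figure that fits the first (BID) test; under the fixed sequence, the power to declare QD is about 77% on the plan's own assumptions

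*Protocol*

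**What the plan says.** **Power.** Protocol section 11.1 (repeated in the section 2 synopsis and in SAP section 3.1) states "With 45 evaluable subjects per treatment group" that "the study has $>85\%$ power", using Fisher's exact test with "2-sided alpha =0.05" and "assuming underlying rates for active and placebo of 30% and 5%, respectively". There is one active rate. The text does not say which dose it stands for, and it does not mention the order of testing. The planned size follows: "Assuming 10% drop-out/non-evaluable rate, a sample size of 50 subjects per treatment arm (approximately 150 total) has been selected".

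**Hypotheses and order.** Protocol section 11.7 names superiority of both BID and QD over placebo as primary hypotheses and handles multiplicity by order: "AKB-9778 15mg twice daily will be tested first, and AKB-9778 15mg once daily will be tested second". SAP section 10.1 makes the condition explicit. After the BID test it says: "If this is found to be statistically significant, then AKB-9778 15 mg once daily will be tested for statistical significance", at the same level.

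**Design.** There is one shared placebo arm: "eligible subjects will be assigned in a double-masked fashion 1:1:1 to one of the 3 treatment groups".

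Neither document gives a power for the second test or for winning both.

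**The concern.** A power statement attached to the study, in a plan with two primary hypotheses, is naturally read as covering both. It does not. QD can be declared significant only when BID is significant too, so its power at the planning stage is the probability of a joint event, which cannot exceed the power of either test alone.

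Protocol section 6.3 gives the QD arm its own question, whether less frequent administration also achieves efficacy, and a third of the subjects are assigned to it. Anyone deciding whether the trial is large enough for that question needs the sequential figure. From section 11.1 they would put the chance of missing a true QD effect of the planned size below 15%.

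**Working it through.** **Inputs**

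| Quantity | Value | Source |
|---|---|---|
| Evaluable per arm | 45 | Protocol 11.1 |
| Active rate, placebo rate | 0.30, 0.05 | Protocol 11.1 |
| Test | Fisher's exact, two-sided 0.05 | Protocol 11.1, 11.7 |
| Allocation | 1:1:1, shared placebo | Protocol 8.3.2 |
| Order and gate | BID, then QD if BID is significant | Protocol 11.7, SAP 10.1 |

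The single active rate of 30% is applied to both doses, because the plan gives no separate rates.

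**Step 1: reproduce the stated figure.** Let Y ~ Bin(45, 0.05) be the placebo responder count. For each y, find the smallest active count c(y) at which Fisher's two-sided p is at most 0.05 in favour of active, and set r(y) = P(Bin(45, 0.30) ≥ c(y)). Then

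single-comparison power = Σ P(Y=y)·r(y).

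**Step 2: the sequence.** Given y, the BID and QD counts are independent, so conditioning on y carries the correlation from the shared placebo arm exactly:

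power to declare QD = Σ P(Y=y)·r_BID(y)·r_QD(y), which is Σ P(Y=y)·r(y)² at equal rates.

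| y | P(Y=y) | c(y) | r(y) | P·r | P·r² |
|---|---|---|---|---|---|
| 0 | 0.0994 | 6 | 0.9974 | 0.0991 | 0.0989 |
| 1 | 0.2355 | 8 | 0.9791 | 0.2306 | 0.2258 |
| 2 | 0.2727 | 9 | 0.9529 | 0.2599 | 0.2476 |
| 3 | 0.2057 | 11 | 0.8353 | 0.1718 | 0.1435 |
| 4 | 0.1137 | 13 | 0.6198 | 0.0705 | 0.0437 |
| 5 | 0.0491 | 14 | 0.4912 | 0.0241 | 0.0118 |
| 6 | 0.0172 | 15 | 0.3653 | 0.0063 | 0.0023 |
| 7 | 0.0050 | 17 | 0.1642 | 0.0008 | 0.0001 |
| 8 | 0.0013 | 18 | 0.0986 | 0.0001 | 0.0000 |
| **Sum** | | | | **0.863** | **0.774** |

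Single comparison: 86.3%, so the stated >85% reproduces. QD under the sequence: 77.4%. A simulation of 400,000 trials gave 86.3% and 77.3%. Treating the two tests as independent would give 0.863² = 74.5%, which is too low because they share a placebo arm.

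**Step 3: what the gate costs.** 86.3 − 77.4 = 8.9 percentage points. This is the probability that QD would pass on its own data but BID would not.

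**Step 4: other scenarios, placebo 5%**

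| Per arm | BID rate | QD rate | BID power | QD power in sequence |
|---|---|---|---|---|
| 45 | 30% | 30% | 86.3% | 77.4% |
| 50 | 30% | 30% | 89.9% | 82.4% |
| 45 | 35% (assumed) | 30% | 94.7% | 83.3% |
| 45 | 40% (assumed) | 30% | 98.4% | 85.5% |

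The 50-per-arm row corresponds to no loss of subjects. The 35% and 40% BID rates are assumptions; they lie inside the 28–46% that the plan cites for intravitreal anti-VEGF treatment.

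For reference, at 30/30/5 the sequential QD power is 84.8% with 52 evaluable per arm and 85.9% with 53. At 10% dropout, 53/0.9 = 58.9, or 59 randomised per arm (177 in total).

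**The case against.** **Per-comparison power is a common convention.** Powering each pairwise comparison and using a fixed sequence to control type I error is ordinary practice, and the sequence here is openly stated. That stands. A reader might infer that the >85% is a calculation error or that the QD comparison is itself weaker; neither follows. The figure reproduces, and QD against placebo taken alone also has 86.3%. What remains is that the text attaches a per-comparison figure to the whole study without saying so.

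**The 77% does not govern how to read a failed QD test.** A reader might infer that a negative QD result would be over-interpreted. The documents do not support that. QD is tested only after a BID win, and given a BID win its power is 77.4/86.3 = 89.6%, above the stated level. If BID fails, QD is not tested, and SAP 10.1 makes that plain. The 77% describes the chance, at the planning stage, of ending with a QD claim.

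**The size depends on the BID rate.** This stands too. If BID is better than 30%, the gate costs less, and at a 40% BID rate sequential QD power reaches 85.5%. But 30% is the rate the plan chose to power on.

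**Much lower figures are not the effect of the gate.** With QD assumed at 25% or 20%, sequential power is 65.2% or 45.4%, but QD alone already has only 70.8% or 48.0%; the gate takes about 6 and 3 points. With placebo at 6.8% or 10.9%, sequential QD power is 63.8% or 35.0%, but the BID test itself falls to 76.7% or 52.1%. Those two control rates come from the macular edema trials summarised in protocol section 4 (sham over 2 years, and a laser group), not from NPDR without center-involved edema. These figures test different assumptions and should not be charged to the testing order.

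**Conclusion.** The point holds as a matter of scope. The stated >85% is correct for one active-versus-placebo comparison, and so for the BID test. It is not the power to declare QD, which the plan also calls a primary hypothesis. On the plan's own inputs (30% in both active arms, 5% placebo, 45 evaluable per arm, two-sided Fisher's exact test at 0.05, QD tested only after a BID win), that power is 77.4%, a loss of about 9 points. The chance of not declaring QD is then about 23%: 13.7% because BID fails and the gate closes, and 8.9% because QD is tested and fails.

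The range is 77% to 82% between 45 and 50 analysed per arm, and up to 85.5% with 45 per arm if BID is assumed to do better than planned. Type I error control is sound. About 77% may be acceptable in a Phase 2 study; it should be stated.

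**What to change.** In protocol section 11.1, the section 2 synopsis and SAP section 3.1, state that:

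- the >85% is per-comparison power and applies to the BID test;
- the power to declare QD under the fixed sequence is about 77%, assuming 30% in both active arms, 5% on placebo and 45 evaluable per arm.

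If lower QD rates or higher placebo rates are shown as well, label them as separate sensitivity assumptions and give the single-comparison power next to each, so that the part due to the gate is visible.

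The cost is one sentence in three places and a less favourable number for QD. Sample size, alpha, test and testing order do not change.
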